We will enroll 40 middle-aged and older men and post-menopausal women with CHD who are overweight or obese and/or have been referred to an outpatient cardiac rehabilitation program at a WFBH site including Wake Forest Baptist Medical Center (WFBMC), Davie Medical Center (DMC), and Lexington Medical Center (LMC). Patients who meet the following inclusion criteria will be asked to participate: 1) documented CHD defined as recent hospitalization for MI/heart attack, coronary artery bypass grafting (CABG), or percutaneous coronary intervention (i.e., angioplasty, stent); 2) age ≥ 40 years; and 3) overweight or obese based on an elevated BMI (≥ 25 kg/m²). Major exclusion criteria include: body weight > 450 lbs; congestive heart failure (ejection fraction $< 35\%$); advanced kidney disease (on dialysis or dialysis anticipated within 6 months); cognitive impairment (Montreal Cognitive Assessment [MoCA] score < 22);²⁹ major depression (Patient Health Questionnaire [PHQ-9] ≥ 20);³⁰ severe pulmonary disease (i.e., oxygen-dependent); significant impairment from a prior stroke or other neurologic disease or injury; high risk for non-adherence (i.e., unwilling or unable to comply with study requirements); current participation in physical therapy or in another research study that prohibits co-enrollment; regular use of weight loss medications (e.g., orlistat); prior weight loss procedure (e.g., gastric bypass, sleeve gastrectomy, gastric banding); women who are pregnant or premenopausal (i.e., menses within past year); drug / substance abuse or excessive alcohol consumption (> 14 drinks/week) within past 6 months; peanut allergy; and milk allergy/lactose intolerance.

Recruitment and Screening of Study Participants

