dynamometer (Jamar, Bolingbrook, IL). Participants will be excluded from performing the test if they report hand pain or recent hand or wrist surgery. **Mobility** will be assessed using the MAT-sf, a 10-item computer-based, self-administered assessment that uses animated video clips of 10 different tasks to illustrate various mobility-related challenges that cover a broad range of functioning.⁴⁸ Participants provide an assessment of their ability to perform each task on the computer by clicking the appropriate response (yes/no, number of minutes, number of times). Scores range from 30 to 80, with higher scores indicative of better mobility.

Health-related quality of life will be assessed using the Medical Outcomes Study Short Form 36 (SF-36), a self-report measure with well-documented psychometric properties across a wide range of populations.⁴⁹ The SF-36 generates eight subscale scores (general health perceptions; physical functioning; role limitations due to physical problems; bodily pain; mental health; role limitations due to emotional problems; vitality; and social functioning) which will be used to derive a physical component summary (PCS) score and a mental component summary (MCS) score, with higher scores indicating more favorable quality of life.

Arterial stiffness will be assessed as carotid-femoral pulse wave velocity (PWV), which is considered the gold-standard measure of arterial stiffness due to its ease of use, high reproducibility, sensitivity to change, and prognostic and clinical utility.⁵²⁻⁵⁸ Carotid-femoral PWV will be measured in the supine position using the SphygmoCor XCEL system (Atcor Medical, Sydney, Australia), which utilizes a piezoelectric Millar tonometer and a thigh cuff to simultaneously record pressure waves in the carotid and femoral arteries, respectively. PWV is calculated by dividing the distance between the carotid and femoral arteries by the pulse transit time.⁵⁹

Blood pressure will be measured with the participant in a seated or supine position after resting quietly for 5-10 minutes. Brachial and central (aortic) blood pressure will be measured using an automated sphygmomanometer and the SphygmoCor XCEL system, respectively.⁸⁴

Hemoglobin A1c will be measured in whole blood using a turbidimetric inhibition immunoassay.

Insulin will be determined by a chemiluminescent immunoassay. Insulin resistance will be estimated using the homeostasis model assessment (HOMA) index.⁶³

Tertiary Outcomes

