- 8) Weight Loss: The risks of caloric restriction are small and include excessive weight loss. These risks will be minimized by the direct involvement of a registered dietitian and medical oversight by the study physician. To ensure safety of study participants, food plans will be tailored to individual preferences, the lowest calorie level permitted will be 1,100 kcals for women and 1,200 kcals for men, and calorie goals will be closely monitored to minimize rapid or excessive weight loss. Weight loss interventions also have the potential to increase risk of hypoglycemia and hypotension. To minimize these risks, study staff will contact the primary care provider of any participant treated with glucose- or blood pressure-lowering medications who develops symptomatic hypoglycemia or hypotension to discuss adjustment or discontinuation of these medications. If a primary care provider cannot be contacted in a timely manner, the study physician may elect to adjust these medications and the personal care provider will be notified by phone and in writing. We have previously completed 8 weight loss trials in a variety of populations with no reports of significant adverse effects.
- 9) Neurovascular Testing: Risks and side effects related to TCD monitoring include reaction from the gel and risk of skin irritation from the TCD headband. However, these are very rare occurrences and no adverse events associated with TCD usage have been reported in the literature. The ECG electrodes may also cause some skin irritation or a mild rash; however, this usually goes away without treatment once the electrodes are removed. Some people may experience discomfort from the finger cuff squeezing their fingers. If this occurs another finger can be used for the assessment. Some fatigue during the sit-stand tests is normal and some people may feel claustrophobic when the non-rebreathing mask is placed over their nose and mouth; if this discomfort persists or if the participant experiences pain, dizziness, or other medical problem, the test will be terminated. Study staff will assess for any signs of pain or intolerance throughout the testing procedure.

Medical Clearance

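### HOMA is planned with no rule for participants who inject insulin, in whom it does not measure insulin resistance; restrict the main HOMA analysis to participants not using insulin before randomization

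*Combined protocol and SAP*

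**What the plan says.** All places are in the combined protocol and SAP.

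- **Secondary Outcomes.** "Insulin will be determined by a chemiluminescent immunoassay". The next sentence reads "Insulin resistance will be estimated using the homeostasis model assessment (HOMA) index". No subgroup is set aside, no marker of the body's own secretion is named, and nothing says whether the assay detects injected insulin.
- **Selection Criteria for Study Participants.** The list opens "Major exclusion criteria include: body weight > 450 lbs; congestive heart failure". It goes on to rule out regular users of weight loss drugs, but it mentions neither diabetes nor insulin nor any other glucose-lowering treatment.
- **Potential Risks, item 8 (Weight Loss).** "Weight loss interventions also have the potential to increase risk of hypoglycemia and hypotension". Staff then turn to the participant's usual doctor, and the rule applies to "any participant treated with glucose- or blood pressure-lowering medications who develops symptomatic hypoglycemia or hypotension to discuss adjustment or discontinuation of these medications".
- **Statistical Analyses.** Everyone randomized is analysed in the assigned group. The fixed effects of the mixed model are sex, obesity severity, site, baseline value, time, group and group by time. Medication use appears only in a general list of factors to be evaluated.
- **Descriptive Variables and Potential Confounders.** Drug names and doses are recorded at screening, and changes are reviewed at 3 and 6 months.

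**The concern.** HOMA combines fasting glucose and fasting insulin, and it reads the insulin as the body's own response to that glucose. In a participant who injects insulin, that reading fails. If the assay detects the product, the result follows the dose. If it does not, the result shows own secretion held down by the dose. Neither is insulin resistance.

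Randomization would balance this on average if nothing changed afterwards. The protocol, however, foresees adjusting or stopping glucose-lowering drugs after symptomatic hypoglycemia, and it names weight loss as a cause of hypoglycemia. Only Rehab+WL receives the calorie deficit. The distortion may therefore differ between arms after randomization.

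What is at stake is one effect estimate and one variability estimate. The Sample Size section says that such estimates are meant to inform a larger trial. With 16 expected per group, a few values carry weight.

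**Working it through.** **Inputs from the documents.** 40 randomized with 20% dropout: 40 × 0.80 / 2 = 16 per group, which reproduces the plan's figure. The plan gives no HOMA mean, SD or effect size, and no share of insulin users.

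**Assumed inputs.** The HOMA formula, because the documents name the index without printing it: glucose (mg/dL) × insulin (µU/mL) / 405. Also the share of insulin users, the fall in measured insulin after a dose cut, and the glucose response. The divisor cancels in every percentage below.

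**1. One affected participant, glucose constant.** At glucose 140, insulin falls from 30 to 21:
- before: 140 × 30 / 405 = 10.37
- after: 140 × 21 / 405 = 7.26, a change of -30%.

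**2. The same with a glucose response.** The HOMA ratio is (1 + glucose rise) × (1 - insulin fall).
- Rise 10%, fall 25%: 1.10 × 0.75 = 0.825, or -17.5%.
- Rise 10%, fall 50%: 1.10 × 0.50 = 0.55, or -45%.
- Rise 40%, fall 25%: 1.40 × 0.75 = 1.05, or +5%.

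The break-even glucose rise is 1 / (1 - fall) - 1, which is 33% for a 25% fall and 100% for a 50% fall. The sign therefore depends on the glucose response. It also depends on the assay: if the injected product is not detected, measured insulin need not fall at all.

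**3. Change in one arm's geometric mean, glucose constant.** The formula is exp(f × ln(1 - d)) - 1, where f is the share of the arm with a dose cut and d is the fall in measured insulin.

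| Who has a cut | f | d | Change |
|---|---|---|---|
| every user, 10% users | 0.10 | 0.20 | -2.2% |
| every user, 25% users | 0.25 | 0.50 | -15.9% |
| one user in five, 10% users | 0.02 | 0.20 | -0.4% |
| one user in five, 25% users | 0.05 | 0.50 | -3.4% |

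These are changes within one arm. Any cuts in the Rehab arm would reduce the difference between arms.

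**4. The same by head count.** Three affected participants among 16, with a 10% glucose rise:
- 25% fall: exp(3 × ln(0.825) / 16) = 0.965
- 50% fall: exp(3 × ln(0.55) / 16) = 0.894.

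**5. Would an arm contain any insulin user?** The probability is 1 - (1 - p)^16. This is 0.82 for p = 10% and 0.97 for p = 20% (p assumed).

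**The case against.** The strongest reply has four parts.

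- **Insulin treatment is never named.** The exclusion list gives only the major criteria, and the risk section speaks of glucose-lowering drugs as a class. This stands as a caveat: that insulin users can enter is inferred, not stated. Still, nothing listed keeps them out, and insulin belongs to that class.
- **A reader might infer that HOMA will fall in Rehab+WL as pure artefact and look like a benefit.** The documents do not support that. Contact with the provider follows only symptomatic hypoglycemia, and it is made "to discuss adjustment or discontinuation of these medications", so a cut is not automatic. The rule covers participants in both arms. Glucose may rise and offset the fall, the assay may miss the product, and a smaller insulin need may partly reflect the better sensitivity under study. What survives is that the index is not valid in these participants and that the arms may be affected unequally.
- **The plan already covers medication and outliers.** It will evaluate medication use, and Data Cleaning will look for outliers and influential points. Neither gives a rule for HOMA. Adjusting for a drug change made after randomization does not turn HOMA into a resistance measure in an insulin user. Deciding on extreme values after inspection leaves the choice open to the result.
- **The stakes are low.** This is correct. The primary outcome is feasibility, power is disclaimed for the measured outcomes, and neither the Objectives nor Table 1 names HOMA. It limits the weight of the point but does not remove it.

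**Conclusion.** The concern holds in a limited form. As written, the plan yields a HOMA value that does not measure insulin resistance in any participant injecting insulin, and nothing in the documents excludes or separates such participants. Drug changes that the protocol itself links to weight loss may make the distortion unequal between arms.

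The direction is not fixed and the size cannot be derived from the documents. The range of about -2% to -16% should not be read as an estimate of bias. It assumes 10-25% insulin users, a 20-50% fall in measured insulin, a cut in every user and constant glucose. With a cut in one user in five, the same formula gives about -0.4% to -3.4%. A reader might also infer a known inflation of the HOMA SD, but the documents give nothing from which to calculate one.

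This is a cheap improvement with low impact. The feasibility outcomes are untouched.

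**What to change.** Add to Statistical Analyses:

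- The main analysis of HOMA, and of fasting insulin where it is read as a resistance marker, includes only participants not using insulin at the screening medication review. The restriction rests on a fact recorded before randomization, so the comparison within that subset remains randomized.
- Two sensitivity analyses follow: one in all participants, and one that also leaves out those who start insulin later. The latter selects on an event after randomization, so it should not be the main analysis.
- Report by arm the number excluded and the changes in glucose-lowering drugs at 3 and 6 months. Other such drugs can also move HOMA, and the restriction does not address them.
- Glucose and HbA1c stay in all participants.

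The medication data are already collected, so the cost is a few lines of text and a smaller sample for this outcome. At an assumed 10-25% users, that is 16 × 0.10 = 1.6 to 16 × 0.25 = 4 participants per group. No change to clinical management is implied.

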Stages and processes of change for weight management will be assessed using the S-Weight and P-Weight, two self-report questionnaires that were designed based on the transtheoretical model.^{27,28} The S-Weight consists of five mutually exclusive items to assess readiness to change in order to lose weight. Respondents are asked to choose the stage that best corresponds to their current weight-loss situation: Pre-contemplation, Contemplation, Preparation, Action, or Maintenance. The P-Weight consists of 34 items measuring readiness to engage in dietary and physical activity behaviors based on four processes of change that are implicated in weight management: Emotional Re-evaluation (13 items), Weight Management Actions (7 items), Environmental Restructuring (5 items), and Weight Consequences Evaluation (9 items). Answers are given on a five-point Likert scale ranging from 1 (strong disagreement) to 5 (strong agreement). Scores for each of the four processes of change can be calculated by summing up the subscale scores. Higher scores reflect greater use of a given process. The use of S-Weight and P-Weight will enable identification of which processes of change individuals use the most according to the stage of change they are in.

Exploratory Outcomes

Cerebral Autoregulation will be assessed via continuous blood pressure (BP) and cerebral blood flow velocity (CBFv) monitoring acquired from noninvasive finger arterial pressure measurements and bilateral transcranial Doppler (TCD) imaging of the middle cerebral arteries (MCA), respectively. CA will be measured at rest and during up to 2 sit-to-stand maneuvers, as described.⁷¹⁻⁷⁴ The single sit-stand

maneuver will consist of 2 min of sitting, followed by 1 min of standing. Data will be averaged over 3 trials. After a brief recovery period, the repeated sit-stand maneuver will be performed at a frequency of 0.05 Hz (10 s sitting, followed by 10 s standing for 15 cycles), which represents the very low-frequency range where CA is most active under normal circumstances.^{75,76} CA will be calculated in the frequency domain using transfer function analysis (TFA) in accordance with Cerebral Autoregulation Research Network (CARNet) recommendations.⁷⁴ Additional CA indices measured in the time domain may also be considered, including the following:⁷⁷ 1) autoregulatory index (ARI);^{78,79} 2) rate of recovery (RoR); and 3) mean flow index (Mx).^{80,81}

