Cardiovascular events and rehospitalizations will be assessed by staff masked to group assignment. Pertinent medical records will be obtained to confirm all events and procedures. Hospitalizations will be categorized using the Clinical Classifications Software system from the Agency for Healthcare Research and Quality (<https://www.hcup-us.ahrq.gov/toolssoftware/ccs10/ccs10.jsp>). The study physician (masked to group assignment) will adjudicate each outcome using standardized criteria.

Analytical Plan

Sample Size

Assuming that at least 50% of eligible patients will be interested in participating in the study and meet the full inclusion/exclusion criteria, we anticipate enrolling 1-2 participants per week. Based on a conservative dropout rate of 20%, we expect a final sample size of 16 per group. While this pilot study is not designed to provide sufficient statistical power to detect differences in the measured outcomes, we will obtain estimates of treatment efficacy and estimate the variability of outcome measures in this population to use in the design of a larger, more definitive trial.

Data Cleaning

We will examine the distributions of the outcome variables and the need for any transformations to approximate conditional normality for further analysis. Summary statistics will be calculated, including means, standard deviations, quartiles, and ranges for continuous variables, and counts and percentages for categorical variables. Range and validation checks will be performed on all variables in collaboration with study personnel. We will examine the distributions of all the variables, identify the potential outliers and influential points, and clean any unreasonable data.

Statistical Analyses

All randomized participants will be included in their original intervention group regardless of compliance with the study protocol (i.e., an “intent to treat” analysis). Chi-square tests will be used to assess group differences in retention and compliance rates. Longitudinal data for the outcome variables will initially be presented graphically (e.g., spaghetti plot) with individual trajectories over time. The graphical displays will help to highlight aggregate patterns of potential scientific interest and identify unusual values. The mixed-model repeated measures ANCOVA model will be used to determine whether Rehab+WL leads to greater improvements in CHD and neurovascular outcomes than Rehab alone. A

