subject random effect will be included to account for the fact that multiple measurements within a participant over time are not independent. Fixed effects will include sex and obesity severity (i.e., the randomization stratification factors), clinical site (WFBMC, DMC, or LMC), the baseline (pre-randomization) value, time (3 or 6 months), the group assignment, and the group by time interaction. Hypothesis tests for intervention effects at the 3- and 6-month study visits will be performed using contrasts of the 3- and 6-month intervention group means. The primary comparison will be based on an intervention contrast at 6 months. Overall comparisons between groups across follow-up visits will be obtained using a contrast to compare average effects across both follow-up visits. Associations with the stage of change (S-Weight) and P-Weight scores will be examined to determine their influence on recruitment, retention, adherence, CHD outcomes, and neurovascular outcomes. If a particular intervention group has a markedly higher dropout rate, we will attempt to identify baseline covariates that predict attrition in secondary analyses. If such covariates can be identified, the analysis of the outcome measure will adjust for those covariates. Other factors that may influence the measured responses to the interventions such as the number of comorbidities, socioeconomic status, time to enrollment, medication use, and magnitude of weight loss will also be evaluated. Differences in intervention process measures (e.g., total volume of exercise) and compliance measures (e.g., attendance at diet and exercise sessions) will also be examined to assess the extent to which these variables contribute to the outcomes.

Human Subjects Protection

Subject Recruitment Methods

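### P-Weight process scores are raw sums over scales of 13, 7, 5 and 9 items, so they cannot show which process a person uses most; use mean item scores for that comparison

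*Combined protocol and SAP*

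**What the plan says.** The paragraph on stages and processes of change, under Tertiary Outcomes, describes the questionnaire: "The P-Weight consists of 34 items measuring readiness to engage in dietary and physical activity behaviors". The items fall into four processes: Emotional Re-evaluation has 13, Weight Management Actions 7, Environmental Restructuring 5 and Weight Consequences Evaluation 9. Each item is answered from 1 to 5, where 5 is the strongest agreement.

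One scoring rule is given: "Scores for each of the four processes of change can be calculated by summing up the subscale scores". It is followed by "Higher scores reflect greater use of a given process". The paragraph closes with what the two instruments are for: they "will enable identification of which processes of change individuals use the most according to the stage of change they are in". No section divides a sum by its number of items, expresses it as a share of its range, or rescales it in any other way.

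The Statistical Analyses section uses the scores once: "Associations with the stage of change (S-Weight) and P-Weight scores will be examined to determine their influence on recruitment, retention, adherence". That sentence goes on to CHD and neurovascular outcomes. It matches the Tertiary Aim, which asks whether motivation and readiness to change influence participation and CHD outcomes.

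**The concern.** Saying which process a person uses most means ranking four scores against each other within that person. Such a ranking makes sense only if equal use gives equal scores. Sums over scales of different length do not have that property, because a longer scale gives a larger number for the same answers. An analyst who follows the written rule for the written purpose would tend to report Emotional Re-evaluation as the most-used process at every stage of change, largely because it has the most items. The protocol presents this pilot as a basis for designing a larger trial, so a profile that partly reflects questionnaire length could be carried forward as a finding about motivation.

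**Working it through.** **Inputs (all from the paragraph on stages and processes of change).** Items per process *k* = 13, 7, 5 and 9; item scores 1 to 5; process score = sum of its items.

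**The plan's own figure.** 13 + 7 + 5 + 9 = 34, which matches the stated total.

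**Ranges and equal endorsement.** The range is *k* × 1 to *k* × 5. At a common item mean *m* the sum is *k* × *m*.

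| Process | Items | Range of sum | Sum at m = 3 | Emotional Re-evaluation sum ÷ this sum, at equal m |
|---|---|---|---|---|
| Emotional Re-evaluation | 13 | 13-65 | 39 | 1 |
| Weight Consequences Evaluation | 9 | 9-45 | 27 | 13/9 = 1.44 |
| Weight Management Actions | 7 | 7-35 | 21 | 13/7 = 1.86 |
| Environmental Restructuring | 5 | 5-25 | 15 | 13/5 = 2.60 |

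At equal endorsement the order is therefore fixed by item count. This needs no assumption about how people answer.

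**When no answer on the other scale can overturn the order.** Emotional Re-evaluation, with item mean *e*, exceeds another scale's maximum when 13*e* > 5*k*, that is *e* > 5*k*/13:

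- against Environmental Restructuring: 25/13 = 1.92
- against Weight Management Actions: 35/13 = 2.69
- against Weight Consequences Evaluation: 45/13 = 3.46

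Above 3.46, no other process can rank first.

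**A worked case.** Someone answers 5 to every Environmental Restructuring item (5 × 5 = 25) and 2 to every Emotional Re-evaluation item (13 × 2 = 26). Raw sums rank Emotional Re-evaluation higher. The item means, 5.0 and 2.0, rank them the other way.

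**Where the order can still go the other way.** With an Emotional Re-evaluation item mean of 3.0 (sum 39), a Weight Consequences Evaluation sum of 40 (item mean 40/9 = 4.44) ranks first. Item count is a strong pull, not a certainty.

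**Illustrative simulation.** All distributions here are assumed; none comes from the documents. Each setting has 200,000 respondents. An item score is a process mean, plus a person effect (SD 0.5), a person-by-process effect (SD as shown) and item noise (SD 1.0), rounded and cut to 1-5. Ties are shared. The process mean is 3 unless stated.

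| Setting | Emotional Re-evaluation first, raw sums | Emotional Re-evaluation first, item means |
|---|---|---|
| Equal use, process SD 0 | 99.2% | 20.9% |
| Equal use, process SD 0.5 | 90.9% | 23.6% |
| Equal use, process SD 1.0 | 76.5% | 24.5% |
| Environmental Restructuring mean 4, SD 0.5 | 90.8% | 8.5% |
| Emotional Re-evaluation mean 2, SD 0.5 | 48.7% | 1.8% |
| Emotional Re-evaluation mean 2 and Weight Consequences Evaluation mean 4, SD 0.5 | 18.1% | 0.3% |

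In the fourth row, raw sums name Environmental Restructuring first in 0.2% of respondents and item means in 72.2%. The direction is the same in every row, but the size varies widely with the assumptions.

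**The case against.** The best defence is that no planned analysis ranks processes within a person. The Statistical Analyses section and the Tertiary Aim speak only of how stage and process scores relate to participation, adherence and outcomes. For each process taken separately, dividing by a constant changes no correlation and no test. This stands. A reader might infer that raw sums undermine the tertiary aim as a whole; the documents do not support that, because the analysis stated for the aim is unaffected apart from units.

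Second, the closing sentence describes what the instruments make possible and is not an endpoint. It might also mean that each process is compared across stages, where raw sums are valid because the item count is constant. This stands in part. The sentence does not define an output table, but its plain sense compares processes with one another, and for that use the only scoring rule supplied gives scores that are not comparable.

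Third, the rule says only how scores can be calculated, and the cited sources for the instruments may add a step. That cannot be judged from the documents. The protocol itself gives an analyst no other rule.

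Fourth, the reach is small. The protocol says that "this pilot study is not designed to provide sufficient statistical power to detect differences in the measured outcomes", and 40 participants over five stages average 40/5 = 8 per stage, so any profile by stage is descriptive at best. This stands and sets the severity.

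**Conclusion.** The point holds, at minor severity. The stated scoring rule does not fit the stated use: at equal endorsement Emotional Re-evaluation always ranks first, and above an item mean of 3.46 it cannot be outranked. Both results follow from the item counts and the 1-5 response range alone, given that each process score is the sum of its own items.

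A reader might go further and conclude that Emotional Re-evaluation wins by item count whatever people answer, or that a particular share of participants would be misclassified. Neither is supported. At or below 3.46 a much more strongly endorsed process can rank first, and every simulated percentage rests on assumed response patterns. No feasibility measure, treatment comparison or single-process association is affected.

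**What to change.** Add one sentence to the paragraph on stages and processes of change, and refer to it in Statistical Analyses: for any comparison between processes, including the most-used process at each stage, score each process as its sum divided by its number of items (range 1-5). An equivalent choice is 100 × (sum − *k*)/(4*k*), which runs from 0 to 100. In the worked case above, that gives 100 × (25 − 5)/20 = 100 for Environmental Restructuring and 100 × (26 − 13)/52 = 25 for Emotional Re-evaluation.

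Keep the raw sums in the report for comparability with other uses of the instrument. It would also help to say whether the most-used process by stage will be reported at all, or only each process across stages.

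The cost is one line of text and one line of code; no new data are needed. One limit remains: means over few items are noisier, so short scales gain slightly when there is no true difference. In the simulated setting with process SD 0, the 5-item scale came first in 29.3% of respondents and the 13-item scale in 20.9%. That is small beside 99.2% for the 13-item scale under raw sums, but it is a reason to show the four mean scores by stage as well as a count of the top-ranked process.
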